# 5.5.2 Handling of Subject Withdrawals or Subject Discontinuation of Study Intervention

If a study participant voluntarily withdraws from the study, the child will continue to receive dental care as usual from his/her personal dentist. If his/her dental care is at CHLA, a routine follow-up appointment will be scheduled as appropriate for his/her next dental cleaning (e.g., six months following the study-related dental cleaning). If a subject voluntarily withdraws while the study is in the enrollment window, we will replace him/her with another subject; if after recruitment and enrollment has closed, no replacement will be made.

No adverse events or unanticipated problems occurred during our R34 pilot study; however, in the event of a serious adverse event or unanticipated problem, as per CHLA's Committee on Clinical Investigations, the investigators and CHLA are not able to offer financial compensation or absorb the costs of treatment. If the serious adverse event or unanticipated problem is not due to the research protocol and the study is still in the enrollment phase, we will replace him/her with another subject. If it occurs after recruitment and enrollment has closed, no replacement will be made.

# 5.6 Premature Termination or Suspension of Study

This study may be suspended or prematurely terminated if there is sufficient reasonable cause. Written notification documenting the reason for study suspension or termination will be provided by the suspending or terminating party to the investigator, funding agency, and regulatory authorities. If the study is prematurely terminated or suspended, the principal investigator will promptly inform the IRB and will provide the reason(s) for the termination or suspension.

Circumstances that may warrant termination include, but are not limited to:

- Determination of unexpected, significant, or unacceptable risk to subjects.
- Insufficient adherence to protocol requirements.
- Determination of futility.

# **6 STUDY INTERVENTION**

# 6.1 Study Behavioral or Social Intervention(s) Description

This study will investigate the impact of adapting the dental environment on the physiological anxiety and negative responses of children with ASD undergoing a dental cleaning. Dental cleaning in a sensory adapted environment (SADE) will be compared to usual treatment for dental cleaning in a regular dental environment (RDE).

Dental cleanings in the *control condition* (RDE) and *experimental condition* (SADE) will take place in a private room in the CHLA Dental Clinic and will each require approximately 15-45 minutes to complete, and will take place four-six months apart. Every effort will be taken to ensure that both cleanings will be performed by the same SADE-trained CHLA pediatric dentistry resident and dental assistant. The SADE environment will be set up prior to the child's entrance into the dental room by a member of the research team.

Table 3 summarizes the specific modifications that comprise the SADE intervention. Specifically, visual, auditory, and deep pressure tactile stimuli are altered in an effort to maximize relaxation. It should be noted that dentists participating in our R34 pilot study indicated that the SADE did not negatively impact their ability to perform the oral cleaning in a regular manner. This was also reported by Shapiro et al. (personal communication, February 25, 2008) who conducted a similar study with children with intellectual and developmental disabilities. This will be empirically tested in the proposed study by including a measure of quality of care. Additionally, the intervention does not require permanent renovations to the dental clinic, as the equipment is portable, requiring approximately 15 minutes to set up or to remove.

Table 3. Components of the SADE Intervention.

Visual	All direct overhead fluorescent lighting and the regular dental overhead lamp will be turned off; dark colored "black-out" removable curtains will cover the windows in the private dental room. The dentist will wear a head-mounted dental lamp directed into the patient's mouth, reducing bright lights shining into the child's eyes. Slow moving visual color effects (Snoezelen) will shine onto the ceiling in the child's visual field.			
Auditory	Auditory stimuli will include rhythmic music projected via a Phillips Portable Speaker System. Music will be either Dan Gibson's Exploring Nature with Music or similar options.			
Tactile / Deep Pressure	The tactile deep pressure stimulus will consist of a butterfly wrap (a modified version of the wrap developed in Israel),  weighted with a regular pediatric dental X-ray vest. The wrap fits around the dental chair and is made of a washable material. The "wings" of the butterfly wrap around the child from shoulder to ankles, providing a deep "hugging" pressure to produce a calming effect.			

Note. See Appendices D and E for pictures of the SADE set-up and "butterfly"

#### 6.2 Administration of Intervention

The private dental room for the SADE will be prepared by trained research team members. Following the set-up of the environment and electrode placement on the study participant's fingers, a three-minute baseline rest period will occur, followed by the dental cleaning led by the CHLA resident. In the RDE, the same research team members will video-record, place electrodes, and obtain EDA recordings, but none of the environmental adaptations will be made.

Each participant will receive a total of two dental cleanings approximately four-six months apart. In this crossover design, one cleaning will be in SADE and the other in the RDE. The duration of each dental cleaning session will be approximately 15-45 minutes.

# 6.3 Procedures for Training Interventionists and Monitoring Intervention Fidelity

Dental room set-up. [name] [name] (Co-I) or her trained designee will be responsible for training research team members on the set-up of the private dental room for both the RDE and SADE conditions. Two trained research team members will prepare the dental treatment room for both conditions, and a checklist will be completed to ensure all equipment has been set-up correctly for each condition [Environment Set-Up Fidelity Form (CRF 24) and the Equipment Set-Up Checklist (Appendix G)].

Dental cleaning sequence of events. [name] or her trained designee will be responsible for training research team members and dental residents about the sequence of events for each dental cleaning (e.g., electrode application  $\rightarrow$  rest period  $\rightarrow$  research-related oral hygiene assessments  $\rightarrow$  traditional CHLA oral examination  $\rightarrow$  intraoral photographs  $\rightarrow$  prophylaxis  $\rightarrow$  intraoral photographs  $\rightarrow$  fluoride application  $\rightarrow$  end of study procedures). At each visit a visual representation will be taped to the wall by the resident for quick reference (See Appendix C).

EDA & video equipment set-up, recording, and coding. [name] or her trained designee will be responsible for training research team members on the set-up and use of both the video and EDA equipment as well as their coding. Reliability of research team members' coding of EDA recordings and video-recordings will be achieved at a *K*=.85 using prior recordings from the R34 pilot study. Recordings from the U01 will be coded by these reliable team members. For quality assurance 25% of EDA codings and 25% of video codings will be compared to coding by [name]. If inadequate reliability is obtained, research team members will undergo retraining. This retraining will include practice coding video and/or EDA data side-by-side with a reliable coder, followed by a retest of reliability (See CRFs 22 and 23 for CDBRS and Scored EDA Forms).

Dental measures. [name] (Co-I) will train residents on oral hygiene measures (Oral Hygiene Index - Simplified, Plaque Index, Gingival Index) and behavioral measures (Modified Anxiety and Cooperation Scale and Frankl Scale) as well as the use of the intraoral camera. [name] or the supervising attending dentist will monitor and check quality of work after the resident has completed each dental cleaning.

ASD diagnosis confirmation. [name] (Co-I) will either conduct the ADOS-2 assessment herself or supervise PhD psychology residents who have been trained by formal courses offered in conjunction with Western Psychological Services in administration of the

Autism Diagnostic Observation Schedule-2 (ADOS-2). Assessments will be videotaped for coscoring and training. [name] will co-score 10% of ADOS-2 assessments using videotapes. If a study participant has previously had the ADOS-2 administered at the CHLA UCEDD, we will accept the ASD confirmation and study results from that previous assessment.

# 6.4 Assessment of Subject Compliance with Study Intervention

Dentist Compliance. The Dentist Recording Form [combination of the Oral Health Indices Form (See CRF 13) and the Behavioral Indices Form (CRF 14)] will be used to record data as well as ensure fidelity to the study protocol. The Oral Health Indices Form includes the Oral Hygiene Index – Simplified (OHI-S), Gingival Index (GI), and Plaque Index. The OHI-S, GI, and Plaque Index will be completed during the oral examination portion of the dental cleaning; the Plaque Index will also be completed by blinded dentists scoring pre-examination and post-examination intra-oral photographs. The Behavioral Indices Form includes the Anxiety and Cooperation Scale and Frankl Scale and will be completed by the dentist directly following the dental cleaning. Additionally, both dental cleanings will be directly observed by research team members, and accidental straying from the protocol will be quietly but quickly corrected.

Participant Compliance. The main measure of participant compliance will be attendance at both scheduled visits. To decrease attrition, as was done successfully in our R34 pilot study, we will contact participants one day, one week, and two weeks prior to their scheduled appointments using the participants' preferred method of communication (e.g., phone call, email, text). All communication attempts will be documented manually on the Call Log Form (CRF 3) and tracked. If an appointment is missed, we will make every attempt to reschedule missed sessions.

Researcher Compliance. Prior to leaving USC OS-OT for a scheduled appointment at CHLA, the research team will complete the Equipment Fidelity Checklist to ensure all necessary equipment is packed for the study protocol. Once at CHLA, the research team will complete the Environment Set-Up Fidelity Form (CRF 24) and the Equipment Set-Up Checklist (Appendix G) to ensure appropriate set-up of both RDE and SADE conditions. Additionally, a research team member will fill out the Visit Completion Form (CRF 25) throughout the dental cleaning to ensure all time measurements have been recorded and video-recording has been completed. A second team member will complete the EDA Flag Form (CRF 26) to ensure that not only EDA has been collected, but marked in real time to designate different dental practices (e.g., beginning of oral exam, beginning of prophylaxis, etc.). Following the dentist completion of the Dentist Recording Form (Oral Health Indices Form and Behavioral Indices Form; CRFs 13 and 14), the research team will also visually inspect the forms to ensure that they have been accurately and fully completed.

#### 7 STUDY SCHEDULE

# 7.1 Screening

# Screening to Determine Eligibility (Day -90 to -15)

CHLA Dental Clinic patients/previous research participants only: In order to determine *initial* eligibility, CHLA dental charts and lists of participants in previous research studies will be reviewed to identify potential participants. As successfully done for our R34 SADE pilot study, a waiver of written or signed consent will be requested from the CHLA IRB for the purposes of determining the initial eligibility of participants so we may identify appropriate children to recruit. Phone contact (see below for greater detail) will be made to families whose children meet this *initial* eligibility (See inclusion/exclusion criteria above Sections 5.1 and 5.2).

# Participants from CHLA (Dental Clinic, UCEDD, Boone Fetter, AltaMed) & LAUSD

- CHLA Dental Clinic patients: We will contact the parent/guardian by telephone to tell them about the research study (CHLA Dental Clinic patients).
- Other CHLA recruitment sites (UCEDD, Boone Fetter, AltaMed), previous research subjects who have agreed to be contacted (not those who participated in R34 SADE Study), and LAUSD: The parent/guardian will contact the research team responding to recruitment brochure/flyer.
  - Following explicit statement of parent/guardian interest in participation, research staff member confirms child participant eligibility (meets inclusion criteria, has no exclusion criteria traits).
  - Following confirmation of child eligibility, if the parent is still interested in participating, an in-person visit is scheduled to conduct the written consent process and complete all questionnaires.

Note. We plan to have a rolling recruitment and enrollment in this study, such that day -30 (for example) for one child will likely be different from day -30 for another child.

#### 7.2 Enrollment/Baseline

# **Enrollment Visit (Visit 1, Day 0)**

- Further explain study protocol and participant responsibilities in greater detail than that discussed on the screening for eligibility phone call. Answer any parent or child questions.
- Verify inclusion/exclusion criteria.
- Obtain and document consent from parent on study consent (parental permission) form. Explain and obtain signature from parents on study HIPAA form.
- Explain and provide parents with California Bill of Rights.
- Obtain and document child assent from child subject on study assent form (if child is available and able to complete/understand form).

• Parental completion of the Parent Bilingual Questionnaire to assess the child and parent's bilingual preference (see Appendix N in MOP).

- Use the Decision Tree for Accepting Child's Data as a guideline to determine if the child is able to give assent based on the parent report (see Appendix O in MOP).
- Parental completion of study questionnaires to obtain demographic information, dental history, anxiety, and sensory over-responsivity. (Complete list of measures to be completed are listed in the Schedule of Events in Appendix A; see CRFs 5-10, 28: Child & Family Information (Demographics), CASI-Anx, SSP-2, SensOR, CFSS-DS, VABS-II Expressive Communication Domain, Dental History Form, Dental Care in Children Questionnaire)
- Child completion of study questionnaires (if able) to obtain information about child perception of dental anxiety. (Complete list of measures to be completed are listed in the Schedule of Events in Appendix A; see CRFs 11-12: CFSS-DS, MCDASf)
- Parents are shown and instructed in the use of the specialized study social story for going to the dentist and participating in the SADE study. Parents are informed that the social story will be mailed to them with instructions two weeks prior to the child participant's first (and second) dental cleaning.
- Parents and children are shown the EDA electrodes and allowed to play with them.

*Note:* This visit (Visit 1) will take place at the participant's home, or if the family prefers, at CHLA, prior to the Autism Diagnostic Confirmation Visit (Visit 2).

#### 7.3 Intermediate Visits

# ASD Diagnosis Confirmation and IQ Testing (Visit 2, Day 1 to 270)

- At the enrollment visit (Visit 1), parents are informed that their child will need to have the ADOS-2 and WASI-II administered at the CHLA UCEDD (parents will also be informed of this during the phone screening prior to this visit). Parent contact information will be provided to [name] and her staff at the CHLA UCEDD for scheduling. A phone screening process will occur during the scheduling call to determine the appropriate ADOS module to be utilized during the ADOS-2 administration. Confirmation of ASD diagnosis through ADOS-2 administration is required to continue with visits for oral cleaning. If child does not meet the ASD criteria based on the ADOS-2, services or treatment at the dental clinic will continue as before but the child will not continue as a research participant nor participate in the study's subsequent visits. If a study participant has previously had the ADOS-2 administered at the CHLA UCEDD, we will accept the ASD confirmation and study results from that previous assessment.
- Child completion of study Assent (if child was not present at Visit 1 and is able to complete/understand form)
- ASD diagnostic confirmation (Autism Diagnostic Observation Schedule 2) and cognitive screen (Wechsler Abbreviated Screening of Intelligence II) administered by [name] or a psychology member of her team.

- All parents/guardians will receive written feedback (by mail) from [name] or a member of her team regarding the general results of the autism and cognitive assessments (see Appendix I in MOP)
- Following completion of Visit 2, randomization into study condition (RDE vs. SADE) for the first dental visit (Visit 3) will occur (see Section 5.4.1 for randomization details).
  - \*\*This behavioral assessment (ADOS-II) must be completed and confirm ASD diagnosis prior to the continuation of study activities and administration of intervention.

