# 5.1 Subject Inclusion Criteria

In order to be eligible for the proposed study, all individuals must meet all of the following criteria:

- Provide signed and dated informed consent (parent permission) and child assent (if appropriate) forms.
- Willing to comply with all study procedures and be available for the duration of the study.
- Male or female, aged 6 through 12 years.
- Have an accompanying parent or guardian who speaks English or Spanish.
- Live within local commuting distance of CHLA.
- Have experienced at least one prior dental cleaning.
- Diagnosed with Autism Spectrum Disorder, based on the Autism Diagnostic Observation Scale, 2nd ed (ADOS-2) as administered by a psychologist from our research team.
- Need an oral cleaning (defined as no oral cleaning within the previous four months).
  - Participants are eligible to be enrolled and complete study Visits 1 and 2 if they
    have had an oral cleaning within the previous four months. However, participants
    will not be eligible to complete Study Visit 3 until a minimum of four months has
    passed following their previous dental cleaning.

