#### 5.4 Treatment Assignment Procedures

# 5.4.1 Randomization Procedures (if applicable)

Following confirmation of ASD diagnosis (administration of ADOS-2), participants will be randomly assigned to the order of treatment, receiving either the Regular Dental Environment (RDE) condition or Sensory Adapted Dental Environment (SADE) condition for their first cleaning. Because we anticipate different rates of participation between gender and age, randomization will be stratified by gender and age (6.0-9.5 years and 9.6-12.11 years) so there is a balance in order of treatment between boys and girls and younger and older children in each order of environment. Randomization will be performed by our PhD biostatistician following a blocked randomization schema for each of the gender-age stratum. We anticipate that the largest stratum will be younger boys (~56% of the sample), followed by older boys (24%), younger girls (15%), and older girls (6%), thus block sizes will vary so that the study team cannot anticipate what the first treatment for a participant will be.

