# 5.5.1 Reasons for Withdrawal

Subjects are free to withdraw from participation in the study at any time upon request.

An investigator may terminate a study subject's participation in the study if:

- Any clinical serious adverse event (SAE), laboratory abnormality, or other medical condition or situation occurs such that continued participation in the study would not be in the best interest of the subject.
- The subject meets an exclusion criterion (either newly developed or not previously recognized) that precludes further study participation.
- The subject cannot tolerate electrodes placed on fingertips.

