# **Intervention Condition 1 (Visit 3, Day 5 to 360)**

- Obtain and document child assent from child subject on study assent form (if child was not present at Visit 1 and is able to complete/understand form).
- Child completion of study questionnaires (if child was not present at Visit 1 and is able to complete/understand form) to obtain information about child perception of dental anxiety.
- Obtain parent-report of current medications of child.
- First dental cleaning will occur, based on randomization of participant into RDE vs. SADE condition.
- Prior to first cleaning, complete Dental Room Set-Up Checklist to ensure fidelity with environment.
- Dentist will photograph child's teeth prior to cleaning.
- Concurrent with the first dental cleaning, record results of dental cleaning on Oral Health Indices Form, complete Visit Completion Form and EDA Flag Form, and collect videorecording and EDA data. (Complete list of measures to be completed are listed in the Schedule of Events in Appendix A; see CRFs 13, 25-26)
- Following administration of dental cleaning:
  - Dentist will photograph child's teeth inside the child's mouth using an intraoral camera.
  - We will obtain dentist's perception of subject's behavior throughout the dental cleaning [Behavioral Indices Form (Anxiety and Cooperation Scale and Frankl Scale); See CRF 14]; complete Usual Dental Care and Planning Form (CRF 15).
  - We will administer child questionnaires (Faces Pain Scale Revised, Dental Sensory Sensitivity Scale, and if in the SADE environment, the Child SADE Acceptance Form; See CRFs 17-19).
  - If in the SADE environment, we will administer the Parent SADE Acceptance Form (See CRF 20).
  - If, based on the Clinical Examination, the child has any dental needs, the dentist will complete the Dental Letter to Parents (Appendix K). A copy will be given to the parent and a copy will be placed in the child's chart and his/her dental findings will be recorded in the child's e-record if the child is a CHLA dental patient.

Note-1: Scoring of intra-oral photographs will take place following the dental cleaning at CHLA by a trained dentist (CRF 16: Quality of Care Recording Form). Coding of video-recordings and EDA recordings will occur off-site (at the designated lab space of the Health Sciences Campus of the University of Southern California) at a later time. (CRFs 22-23: Children's Dental Behavior Rating Scale & Scored EDA Form)

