# 12.4 Final Analysis Plan

Descriptive statistics will be performed for all variables of interest to describe the participant population at baseline, including attrition rate and missing data, to compare those randomized to SADE first vs. those randomized to RDE first. We anticipate a low attrition rate (~10%) and will impute missing data for intent-to-treat analyses using Markov Chain Monte Carlo (MCMC)

imputation with multiple values imputer for each missing value averaged for an estimation for analyses. Bivariate associations between outcomes (physiological anxiety and children's negative behavioral responses), environment (SADE or RDE), and covariates (age, gender, order of visit, autism severity, IQ, and sensory sensitivity) will be described. The primary objective of determining difference between dental environments will be tested using intent-to-treat models examining the within-subject factor of dental environment (SADE vs RDE) using repeated measures ANCOVA for each outcome. *A priori* covariates include age (continuous), randomized order of visit, gender, and temperature. Other participant characteristics that are unbalanced between order of visits will be included as covariates *ad hoc*.

The secondary objective of examining the mediating effect of physiologic response on behavioral outcomes will be tested by first examining the bivariate relationships between EDA and behavioral outcomes, and then adding EDA estimates (SCL and NS-SCR) to models of dental environment difference on behavioral outcomes, and examining the change in the within group coefficients. A change in coefficient >15% will be considered evidence of mediation. While we have several outcomes, we specify only one mediator, thus we will apply a rational approach to examination of multiple outcomes, and will assess the fidelity of our study by estimating effect sizes (Cohen's d) of the dental environment before and after the mediation factors are assessed to confirm that statistical results were supported by clinical relevance of findings. If physiological anxiety does mediate the environment's effect on negative behavioral responses, we anticipate that the anticipated effect of environment will be eliminated once we add in EDA to the models specified in Hypothesis 2. Analyses will be performed using SPSS (v.22); a priori two-sided  $\square = 0.05$ .

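### Children randomised after Visit 2 but never cleaned have no outcome in either environment; the plan would impute both values and average the draws, understating the standard error

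*Combined protocol and SAP*

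**What the plan says.** **Time of randomisation.** Section 7.3, under Visit 2: "Following completion of Visit 2, randomization into study condition (RDE vs. SADE) for the first dental visit (Visit 3) will occur". Section 5.4.1 agrees: "Following confirmation of ASD diagnosis (administration of ADOS-2), participants will be randomly assigned to the order of treatment". Neither names a further eligibility check at that point.

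**Four-month rule.** Section 5.1 lets a child with a recent cleaning enrol and complete Visits 1 and 2. Such a child "will not be eligible to complete Study Visit 3 until a minimum of four months has" passed since that cleaning.

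**Checks of the criteria.** Section 7.2 verifies inclusion and exclusion criteria at Visit 1 (Day 0). The next related step is at Visit 3: "Obtain parent-report of current medications of child". Section 5.2 excludes children on anticholinergic drugs because these may alter EDA, the primary outcome; orthodontia is also an exclusion.

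**Late findings.** Section 5.5.1 lets the investigator end participation if "The subject meets an exclusion criterion (either newly developed or not previously recognized) that precludes further study participation". Section 5.5.2 replaces voluntary withdrawals while enrolment is open, and children with certain serious events unrelated to the protocol. It does not mention children terminated for a new exclusion, or say whether a replaced child stays in the intent-to-treat set.

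**Analysis.** Section 12.4 says the team "will impute missing data for intent-to-treat analyses" by MCMC, drawing several values for each missing one and averaging them. Children with no cleaning at all are not treated separately.

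**Status.** Note-3 under Visit 4 in Section 7.3 reports that by March 2020 recruitment was complete and all participants had finished Visits 1 to 3, with 25 second cleanings outstanding.

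**The concern.** In a two-period crossover, a child lost after the first period still has one observed outcome. A child lost between randomisation and the first period has none. The sequence above allows such losses, because allocation comes before the wait for the first cleaning and before the medication question.

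The harm comes from how these children would be analysed. With neither visit observed, both of the child's EDA values come from the imputation model, and so does the difference between them. That difference says nothing new about the environments. Averaging the draws also removes most of the scatter that proper multiple imputation would keep. The child then adds one to the sample size and almost nothing to the estimated variance, so the test of the primary outcome becomes anti-conservative.

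**Working it through.** **1. The plan's sample size.** Section 12.2 gives 165 pairs, a within-child d of 0.22 and 80% power. The paired formula is n = ((z_alpha + z_power)/d)². At two-sided 0.05:

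- n = ((1.960 + 0.842)/0.22)² = 162.2, so 163.
- The exact t version gives 165, which reproduces the plan's figure.

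The plan recruits 220, so the margin is 220 - 165 = 55 children, or 25%. The stated 10% attrition alone would give 165/0.9 = 184 recruited, or 220 × 0.9 = 198 pairs.

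**2. Length of the wait.** The windows are "ASD Diagnosis Confirmation and IQ Testing (Visit 2, Day 1 to 270") and "Intervention Condition 1 (Visit 3, Day 5 to 360").

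- Largest gap: 360 - 1 = 359 days.
- If Visit 2 falls on Day 270: at most 360 - 270 = 90 days.
- Visit 4 closes on Day 450 and cleanings are at least about 120 days apart, so a child on schedule has Visit 3 by about Day 330.
- A child cleaned just before Visit 1, with Visit 2 on Day 1, waits about 120 days after Visit 2.

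The documents give no typical wait and do not say how soon after Visit 2 allocation happens.

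**3. Number affected (assumed).** The documents give no loss rate for this gap. At 2-5% of 220 the count is 4.4 to 11, taken as 4 to 11 children. That is about 8-20% of the 55-child margin (4.4/55 to 11/55).

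**4. Effect on the standard error, limiting case.** Suppose N = 220 are analysed, n = 220 - k have real differences, and each of the k imputed differences equals the observed mean. The point estimate is unchanged. The imputed children add nothing to the sum of squares, but they raise the degrees of freedom and the divisor:

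SE reported / SE correct = √[ (n - 1)/(N - 1) × n/N ]

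| k | n | ratio | understatement | nominal critical t (219 df) | effective critical t | actual two-sided error |
|---|---|---|---|---|---|---|
| 4 | 216 | √(215/219 × 216/220) = 0.982 | 1.8% | 1.971 | 1.935 | 5.4% |
| 11 | 209 | √(208/219 × 209/220) = 0.950 | 5.0% | 1.971 | 1.872 | 6.3% |

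The effective critical value is 1.971 times the ratio. The actual error is its two-sided tail on n - 1 degrees of freedom.

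**5. Effect on power.** Suppose 5% (11) of 220 are lost before Visit 3 and 10% of the remaining 209 afterwards. That leaves 188 pairs and power 0.85 at d = 0.22, two-sided 0.05. With no loss before Visit 3, the figures are 198 pairs and 0.87. If randomisation came after the wait, the same 11 children would be lost before it, and the pairs would still be 188. For a fixed number recruited, only the intent-to-treat denominator and the amount imputed depend on when children are randomised.

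**The case against.** The strongest objection is that the timing can no longer be changed. Note-3 in Section 7.3 says all participants had completed Visits 1 to 3 by March 2020, so no child is left to randomise. That stands. It does not settle the analysis question: the note does not show whether randomised children were lost, replaced or no longer counted as participants before that date.

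Several stronger readings are tempting, and the documents do not support them:

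- **That the four-month rule makes randomised children ineligible.** It only defers Visit 3. Section 5.5.1 concerns exclusion criteria, and the four-month rule is an inclusion criterion. Losses come from drop-out or a newly found exclusion.
- **That children typically wait about a year.** The 359 days is the extreme of two windows. Completion of Visit 2 is the earliest time for allocation, not its date.
- **That these losses use up a 22-child (10%) allowance.** The plan's margin from 220 to 165 is 55 children, and some withdrawals are replaced.
- **That nearly all such losses could have been avoided.** The plan gives no causes or rates. A telephone re-check would not detect electrode intolerance, or a drug started after the call.
- **That nothing before the cleaning needs early allocation.** The social story is mailed two weeks ahead and is used to explain the SADE components. Whether it differs by condition is not stated.
- **That lost slots in the small strata bias the comparison.** Environment is compared within child, and order, gender and age are planned covariates.

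**Conclusion.** The concern holds as an analysis point of modest size. The plan allows children to be randomised with neither outcome observed, and its imputation rule as written would generate both values. In the limiting case, 4 to 11 such children make the standard error about 2-5% too small and raise a nominal 5% two-sided error to about 5.4-6.3%.

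These figures rest on three assumptions: a loss of 2-5% of 220, which the documents neither give nor exclude; 220 children analysed, with all the others having observed differences; and averaged imputations equal to the observed mean difference. If no randomised child was lost before Visit 3, the effect is zero. Draws that keep some scatter after averaging would make it smaller.

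A reader might infer that the trial loses power, or that its randomisation is compromised. Neither follows. For a fixed number recruited, the timing leaves pairs and power unchanged, and children lost before either cleaning leave no observed outcome to distort the within-child comparison.

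**What to change.** In Section 12.4, before database lock:

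- State that outcomes will not be imputed at both visits for children who were randomised but had neither cleaning.
- Base the primary within-child comparison on children with at least one observed cleaning.
- Report the never-cleaned children by randomised order and by gender-age stratum, with reasons, including any who were replaced under Section 5.5.2. State the number even if it is zero.

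The cost is SAP wording and a count from existing records. The analysis set becomes slightly smaller and the interval slightly wider: by about 2-5% under the assumptions above, which is the width it should have had.

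For a future trial of this design, randomising after an eligibility re-check shortly before the first cleaning would turn losses up to that check into pre-randomisation losses, at the price of shorter notice of the allocation. It is not a change this trial can make.
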